-------------------------	--

[figure not shown]
Immunogenicity assessments	
After complete decay of radioactivity, one out of two serum samples per time-point will be shipped to the central laboratory and analyzed by ELISA to determine the rhAnnexin V-128 concentration in serum (method detailed in the Laboratory Manual).
 
Assays for anti-rhAnnexin V-128 IgG and IgM antibodies will be performed in serum samples by ELISA. For this purpose 10mL blood samples will be collected at baseline, at Day 30 ± 3 days and at Day 56 ± 14 days. An additional sample is required 3 months after the first administration of the 99mTc-rhAnnexin V-128 (Day 90 ± 14 days) in case of positive anti-Annexin antibodies outcome in previous examinations. Serum will be prepared, divided into six aliquots and frozen (-80°C) until complete decay. Three out of six serum samples per time-point will be then shipped to the centralized laboratory, where the analysis for anti-rhAnnexin V-128 antibodies will be performed (methods detailed in the Laboratory Manual).
 
24 hours after each treatment injection (at Day 2 and Day 43), each patient will be interviewed over the phone (in face to face meeting at Day 2 for patients who will participate into the PK and dosimetric sub study) in order to inquire if they experienced signs or symptoms of allergic reactions (edema, rash). If this is the case, Adverse Event(s) should be reported and recorded in the Case Report Form.

Safety and tolerability	Adverse events will be collected in the Case Report Form (CRF).

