### **3 STUDY DESIGN**

#### **Study Outline**

This is a monocentric, open label, Phase I-IIa study.

Patients who have signed the informed consent and are eligible for study participation according to the inclusion and exclusion criteria will receive a single intravenous bolus of 99mTc-rhAnnexin V-128 on Day 1 and a single intravenous bolus of 99mTc-rhAnnexin V-128 6 weeks later (+/- 2 weeks).

All patients will start a new RA or AS treatment on Day 2.

In order to minimize the risks for the study population, patients will be enrolled with a minimum of 2-week interval.

Details on study assessments are provided in Protocol Section 6 and Table1.

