### **Details on treatment of the patients:**

Patients with RA will be diagnosed based on ACR/EULAR10 and will thereafter be evaluated with DAS 28. Patients with AS will be diagnosed based on the ASAS criteria. Each patient will be anonymized and identified with a patient ID number.

A unique subject identification number (Patient ID) will be assigned at the start of the Screening Period to each subject who signs the informed consent form until the study termination of the patient. This number will identify the subject throughout the study.

Patient IDs will include the 2-digit country code number (SW) and a 3-digit subject number (ex: SW001 for first subject In).

In both groups of patients – i.e. RA and AS patients – the introduction of a Bi-DMARD treatment should be indicated at the moment of inclusion in the study. The Bi-DMARD therapy should start on Day 2 of the study. RA patients must have been treated at least with one DMARD (methotrexate, leflunomide and sulfasalazine) or a combination of them in the last 3 months – before inclusion - and this/these DMARD(s) will be continued in this study. Otherwise, RA patients must have been previously treated with Bi-DMARD before administration of the new Bi-DMARD treatment. The non-response of the previous Bi-DMARD treatment must be documented.

AS patients must at least have been treated with NSAID in the last 3 months before inclusion and they

should be under the same NSAID treatment during the last 4 weeks before inclusion.

For RA patients, anti-tumour necrosis factor (TNF) antibodies, anti-interleukine 6 (IL-6) antibodies and abatacept therapies are to be considered and are authorized in Switzerland as first line Bi-DMARD agents in RA. On the contrary, anti-CD 20 positive lymphocytes antibodies can only be used, if one anti-TNF therapy failed.

In the AS patients group, only anti-TNF antibodies can be considered, if NSAID are not sufficient.

Ten patients enrolled in the study will be asked to participate in a dosimetry and PK sub-study, irrespective of the group they are part of (RA or AS).

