### **Study Medication Dose, Mode of Administration, Batch Number**

The "Kit for preparation of 99mTc-rhAnnexin V-128 for injection" consists of 1 patient dose.

The single dose vial (0.40 mg rh-Annexin V-128) will be reconstituted with 2 mL ± 0.2 mL containing 740 MBq ± 74 MBq (20 mCi ± 2 mCi) of 99mTc. The labelling reaction requires 90 minutes and the reconstituted radiolabelled product is stable for 6 h. For the purpose of this study, it is recommended to administer the reconstituted solution within 4 hours after completion of the labelling reaction,

Patients will receive 2 administrations of 99mTc-rhAnnexin V-128 , one on day 1 and one on day 42 (±14 days).

When investigational product is received at the site, the Investigator, Pharmacist or authorized designee shall check for accurate delivery and acknowledge receipt by signing and dating the documentation provided by the Sponsor and returning it to the Sponsor or designee. A copy of this documentation shall be retained for the Investigator file.

The dispensing of the investigational product shall be carefully recorded on an investigational product accountability form provided and an accurate accounting must be available for verification by the Clinical Research Associate at each monitoring visit.

Unused investigational product must not be discarded or used for any purpose other than the present study.

The Clinical Research Associate will periodically collect the Drug Accountability Forms and will check all investigational product (both unused and used) before making arrangements for authorizing their destruction at the investigational site.

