4.9 Safety

4.9.1 Adverse Events

AEs will be reported from signing the informed consent onwards until the last study-related procedure. If the information of an untoward medical occurrence is collected before starting the intake of study medication, this information will be listed as a pre-treatment AE during statistical analysis. AEs that occurred after the first intake of study medication will be considered as treatment emergent for the analysis.

All AEs occurring during the study are to be followed up until resolved or judged to be no longer clinically significant, or until they become chronic to the extent that they can be fully characterized. An assessment should be made at the last study-related visit for each patient (See Study Protocol for more details).

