4.9.2 Laboratory Parameters

Laboratory tests (haematology, coagulation, blood chemistry and urinalysis) will be monitored before and after the Day 1 visit, with additional samples at 24 hours (only for patients participating to the PK substudy), 30, 42 and 90 study day.

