7.8 Adverse Events

All AEs reported after the first dose (treatment emergent adverse events, TEAEs) will be summarized and their occurrence rate, will be presented by MedDRA system organ class (SOC) and preferred term (PT), overall and by worst severity level. Within a SOC, PT will be presented in descending order of overall occurrence.

Relationship to the investigational product will be assessed by presenting separately all AEs and AEs at least possibly related to study drug (i.e. cause = study treatment and relationship = probable or possible).

Pre-treatment AE will just be presented in the listings.

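### The SAP's adverse event tables do not separate onset before and after the Day 2 start of the biologic, or by tracer injection

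*SAP*

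**What the plan says.** The only primary objective (Protocol section 2) is the safety and tolerability of imaging with the tracer. SAP 6.1 evaluates it by adverse events, abnormal laboratory tests, and changes in ECG and vital signs. The tracer is injected on Day 1 and again at Day 42 ± 14 days.

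On the disease treatment, the Protocol's Study Outline says "All patients will start a new RA or AS treatment on Day 2". Its details on patient treatment add, for both disease groups, "The Bi-DMARD therapy should start on Day 2 of the study". No group goes without the tracer or the biologic.

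On adverse events, SAP 4.9.1 says "AEs will be reported from signing the informed consent onwards until the last study-related procedure" and "AEs that occurred after the first intake of study medication will be considered as treatment emergent for the analysis". SAP 7.8 follows: "All AEs reported after the first dose (treatment emergent adverse events, TEAEs) will be summarized". The tables in SAP 7.8.2 and 10.1 split these events by disease group, MedDRA class and term, severity, seriousness, discontinuation, death and relationship to study drug. Exposure is summarised by first and second injection (SAP 7.6, Table 14.1.7); adverse events are not. Onset day is counted from the first dose only (SAP 7.8.2).

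On laboratory tests, SAP 4.9.2 plans sampling before and after Day 1, "with additional samples at 24 hours (only for patients participating to the PK substudy), 30, 42 and 90 study day". SAP 7.9 tabulates each visit and its change from a baseline that SAP 7.1.5.5 places before the tracer.

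On early reactions, the Protocol Synopsis says "24 hours after each treatment injection (at Day 2 and Day 43), each patient will be interviewed over the phone". Sub-study patients are seen in person on Day 2 instead.

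**The concern.** A biologic newly started in every patient can itself produce rash, injection-site reactions, infections, raised transaminases or cytopenias. In one pooled period these sit beside any tracer effects, and a reader of the overall tables cannot see which events began before the biologic.

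The reverse error is also possible. A tracer reaction appearing on Day 2 may be ascribed to the drug started that day. The allergy interview and the sub-study's 24 h laboratory tests, ECG and vital signs all fall on Day 2, and neither document says whether they come before or after the first Bi-DMARD dose.

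What is at stake is how the primary safety result can be read. No sample size or test depends on it: SAP 7.7 plans no formal safety testing.

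**Working it through.** 1. **The plan's own figure.** The one sample-size calculation reproduces: 20 / (1 − 0.10) = 22.2, rounded up to 23 recruited. This point does not change it.

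2. **Share of the event window before the biologic.** Inputs: first injection on Day 1, planned biologic start on Day 2, last scheduled visit on Day 90 ± 14. Share = 1 / (last day − 1).
   - Day 90: 1/89 = 1.1%, so 88 of 89 days (98.9%) follow the planned start.
   - Day 76: 1/75 = 1.3%. Day 104: 1/103 = 1.0%.
   - If events stopped at the Protocol's end-of-study point, 18 days after an injection on Day 42 (Day 60): 1/59 = 1.7%.

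3. **Second injection.** Day 28 to Day 56, less Day 2, means 26 to 54 days after the planned biologic start. By plan, no part of the period after injection 2 is free of the biologic.

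4. **Laboratory panels.** Outside the sub-study there are three scheduled post-dose panels (Days 30, 42 and 90), and none precedes the biologic. The first, at Day 27 to 33, comes 25 to 31 days after planned start. Inside the sub-study there are four, of which at most one (24 h) could precede it. With 10 patients in each category as planned, 10×3 + 10×4 = 70 panels, and at most 10 (14%) could be free of the biologic. All 10 fall on its start day.

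5. **How far a pooled incidence can hide a tracer effect.** The documents give no event rates, so these are assumptions. Let b be the proportion of patients with an event from the biologic or background, and t the proportion with one from the tracer, taken as independent. Pooled incidence = 1 − (1 − t)(1 − b). With 20 patients:

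| b | t = 0 | t = 10% |
|---|---|---|
| 30% | 6.0 | 7.4 |
| 50% | 10.0 | 11.0 |
| 70% | 14.0 | 14.6 |

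6. **What a pre-biologic row would hold.** At a constant background hazard over 89 days, the one-day probability is 1 − (1 − b)^(1/89). For b = 30%, 50% and 70%, the expected number of patients among 20 is 0.08, 0.16 and 0.27. Background events would therefore rarely appear there. A row with no events would still be weak evidence: the one-sided 95% upper bound, 1 − 0.05^(1/n), is 13.9% for n = 20 and 17.1% for n = 16 (80% of 20, the level in SAP 4.2).

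7. **SAP rules that affect any split by time.** Under SAP 7.8.2, an event with a missing start day in the month of first dose is dated to the first dose, which would move a later biologic reaction into the pre-biologic period. In other months a missing day becomes the first of the month, which can place an event before injection 2. Under SAP 7.8.1, repeats of one preferred term count once per patient at the worst attribute, so early and late occurrences merge.

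**The case against.** The strongest reply is that the plan does separate tracer from biologic. SAP 7.8 presents events at least possibly related to study drug apart from all events. SAP 7.8.2 adds tables by relationship, the Table 14.3.1.1 shell has rows for adverse drug reactions, and Listing 16.2.7.4 covers drug-related events. Treatment emergent is a label of timing, not of cause. A reader might infer that a rash caused by the biologic will be reported as a tracer reaction; the documents do not support that. What remains is that the separation is investigator judgement, open label and without a comparator. The relationship shell has only two classes, related and not related, so attribution to the biologic is never tabulated. The option of another treatment as cause is shown only on the SAE form.

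A reader might also infer that laboratory changes are pooled as treatment emergent. They are not: SAP 7.9 shows them by visit. Their limitation is the timing of the samples.

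It may also be said that Day 2 is the only early checkpoint. That overlooks the Day 1 ECG and vital signs taken in all patients. Whether these precede or follow the injection is not stated, so they may or may not supply data free of the biologic.

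Finally, onset day is already planned and medications are listed by patient, so a reader could rebuild the split. That holds approximately for patients who start exactly on Day 2, but it leaves the work to the reader and ignores actual start dates. The confounding does come from the design, and no table can remove it.

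**Conclusion.** The point holds as a gap in presentation of the primary safety endpoint. About 99% of the treatment-emergent window to Day 90 is also planned biologic exposure, and no listed table shows onset relative to the biologic or to each injection. Relationship tables reduce the problem but do not close it.

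This rests on two assumptions: that patients start the biologic about 24 h after injection 1, as planned, and that events are collected to about Day 90. The incidences in the illustration are assumed.

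Two stronger conclusions should be avoided. Events within 24 h of injection 2 might be read as attributable to the tracer, but those patients would by plan have been on the biologic for 26 to 54 days. Nor should the safety summary be limited to the short windows, because a later tracer effect would be lost. The plan itself looks for late effects through antibody samples at Day 30 and Day 56, and at Day 90 after an earlier positive result.

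**What to change.** **SAP 7.8 and 10.1.** Add one descriptive table of treatment-emergent events and one flag in the adverse event listing:
- Class onset as before, on the same calendar day as, or after the first Bi-DMARD dose, using the actual start date from the concomitant medication record. SAP 4.7 records RA and AS treatments, and SAP 7.13 already uses medication dates.
- Class onset also as after injection 1 or after injection 2, with a row for onset within 24 h of each injection labelled 'temporally close to tracer'. Where only dates are held, state how 24 h is approximated.
- Count a patient once per preferred term within each period, so that a recurrence after the biologic does not hide an earlier event.
- Show events with imputed onset dates on a separate line.
- Keep the all-event and by-relationship tables unchanged.

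**SAP 7.9.** Footnote the Day 30, 42 and 90 results as on Bi-DMARD. Show the sub-study 24 h results separately, using clock times from source records, where available, to establish whether each sample came before the first Bi-DMARD dose.

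A new CRF time field would come too late: SAP 4.2 puts the end of recruitment at the end of September 2017, and the SAP is dated January 2018.

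The cost is one table, one flag, some footnotes and a limited source check. No visit, dose or sample size changes. The pre-biologic rows will be sparse, and the text should say that they describe timing rather than establish cause.

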## **Follow-up of Adverse Events**

All AEs occurring during the study are to be followed up until resolved or judged to be no longer clinically significant, or until they become chronic to the extent that they can be fully characterized. An assessment should be made at the last study-related visit for each patient. Certain long-term AEs cannot be followed until resolution within the settings of this protocol. In these cases follow-up will be the responsibility of the treating physician.

Since it is unpredictable how long such a follow-up might take, data from this follow-up generated after the patient's last study-related visit will be recorded by the Investigator. Full details regarding this follow-up will be described in the Clinical Study Report, if necessary.

If during AE follow-up the case has progressed to the level of "SAE", or if a new SAE whose relationship to the study medication could not be ruled out is observed, the situation must be reported immediately by the Investigator becoming aware of the information (considering that the "date of SAE onset" is the date of the first manifestations of that AE).

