7.7 Evaluation of Safety

The safety analyses will be performed on the Safety set. All safety analyses will be performed considering the treatment received by the subjects.

Safety will be evaluated by abnormal renal function, hepatic function and coagulation laboratory tests and treatment emergent serious and non-serious adverse event assessments over the study period.

No formal hypothesis testing will be carried out.

No imputations will be used in the analysis of safety data.

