7.8.2 Adverse Events Tabulation

Calculated AE duration will be indicated in the listing.

Onset day of an AE will be calculated if both the AE start date and date of dosing are complete and is calculated as:

- Onset day for AE = (AE start date – Date of first dose) + 1 (only if AE start date \geq First dose date)

Duration of an AE will be calculated if both the AE stop and start dates are complete and is calculated as:

- Duration of an AE = (AE stop date – AE start date) + 1

In cases where the start date of an AE is completely known but the AE has not yet resolved at the end of the study, duration of an AE will be calculated as:

- Duration of an unresolved AE = (Study termination date – AE start date) + 1

These observations will be flagged in listings with a greater than sign (i.e. $>$) prior to presentation of the duration.

In case of AE partial dates: if only the day is missing then the first day of the month will be used for start dates and the last day of the month will be used for end dates. In case the AE started on the same month than the first dose and the AE start day is missing, the partial date will be replaced by the first dose date.

If the month is missing no imputation will be done.

If duration of an AE cannot be calculated, the information will be missing from the listing.

Incidence rates, frequencies and summary tabulations will be provided for:

- All TEAEs
- All Treatment Emergent Serious AEs (TESAEs)
- All Treatment Emergent Serious AEs (TESAEs) by severity
- All TEAEs leading to permanent treatment discontinuation
- All TEAEs by severity
- All TESAEs by drug-event relationship
- All TEAEs by drug-event relationship
- All TEAEs leading to death

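### The SAP's two treatment-emergent AE rules disagree, neither covers worsening after injection, and the partial-date rules can misclassify events in the TEAE incidence tables

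*SAP*

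**What the plan says.** Two statements define a TEAE. SAP 4.9.1 goes by occurrence: "AEs that occurred after the first intake of study medication will be considered as treatment emergent for the analysis". SAP 7.8 goes by report: "All AEs reported after the first dose (treatment emergent adverse events, TEAEs) will be summarized". A third criterion sits beside them. In SAP 4.9.1, as in the Protocol's AE definition, if the information is collected before study medication starts, "this information will be listed as a pre-treatment AE during statistical analysis". SAP 7.8 adds: "Pre-treatment AE will just be presented in the listings".

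AEs are collected from consent, and the study schema allows a four-week screening window, so pre-injection AEs are to be expected. Protocol section 9 (Follow-up of Adverse Events) foresees an AE that progresses to an SAE. It states that the SAE onset date "is the date of the first manifestations of that AE".

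SAP 7.8.2 sets the date rules. A start with only the day missing goes to the first of the month. If the month is that of the first dose and "the AE start day is missing, the partial date will be replaced by the first dose date". Further, "If the month is missing no imputation will be done". SAP 7.7 says: "No imputations will be used in the analysis of safety data". SAP 7.1.2 says the same of safety data.

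**The concern.** Safety and tolerability is the only primary objective. AE assessment is the first endpoint in SAP 6.1, and SAP 7.7 evaluates it as treatment-emergent AEs. The rule that sorts events into or out of the TEAE tables should therefore give one answer from one set of data.

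As written, two programmers following different sections could produce different incidence tables. An event that is mild at screening and serious after injection can be left out of the serious-TEAE counts. An event known to have ended before exposure can be counted as treatment emergent. The errors run in both directions, so they cannot be defended as consistently cautious.

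**Working it through.** **1. The rules side by side**

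| Case | SAP 4.9.1 (occurrence) | SAP 7.8 (report) |
|---|---|---|
| A. Starts before injection, first mentioned afterwards (for example at the 24-hour contact) | Not a TEAE | TEAE |
| B. Recorded at screening, worse or serious after injection, same record and onset kept | Not a TEAE | TEAE only if the later report counts as a new report |
| C. As B, but a new CRF record is opened at the change | TEAE | TEAE |
| D. Day missing, dosing month, known stop before first dose | TEAE by date substitution | Depends on report date |
| E. Month missing | Undefined | Depends on report date |

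Case A also fails the pre-treatment criterion in 4.9.1, because the information was not collected before dosing. Within that section it belongs to neither class. Whether B or C applies is not stated anywhere in the documents. The worst-severity rule in SAP 7.8.1 does not rescue B, because SAP 7.8 tabulates only TEAEs.

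**2. Worked dates, first dose assumed to be 20 June**

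- Onset 10 June, serious on 25 June, onset kept: 10 June is before 20 June, so not treatment emergent under 4.9.1.
- Start June (day missing), stop 15 June: start set to 20 June, so a TEAE. If the substituted date is used in the duration formula, (15 − 20) + 1 = −4 days.
- Day missing in May: start set to 1 May, not a TEAE (correct).
- Day missing in July: start set to 1 July, TEAE (correct).
- Month missing: no date and no class under 4.9.1.

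**3. Direction of the missing-day rule**

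A post-dose onset in the dosing month is set to the first-dose date, and one in a later month to the first of that month. Neither is before the first dose. Over all 365 first-dose days and onsets 0 to 90 days later, 0 of 365 × 91 = 33,215 are called pre-treatment.

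For onsets 1 to 28 days before dosing there are 365 × 28 = 10,220 combinations. Those in the dosing month number 462 for each 31-day month, 434 for each 30-day month and 378 for February: 7 × 462 + 4 × 434 + 378 = 5,348, or 52%, all called TEAEs. This assumes that the day is missing and that onset is uniform over four weeks. It shows direction only and does not estimate anything in this trial.

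**4. What one patient is worth**

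SAP 4.2 plans 20 evaluable patients with about 10% not completing. 20 / 0.90 = 22.2, rounded up to 23, which reproduces its figure. After recruitment stopped, the floor is 0.80 × 20 = 16. Exact (Clopper-Pearson) 95% limits, with upper limit 1 − 0.025^(1/n) for zero events:

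| n | 0 events | 1 event |
|---|---|---|
| 16 | 0% (0 to 20.6%) | 6.3% (0.2 to 30.2%) |
| 20 | 0% (0 to 16.8%) | 5.0% (0.1 to 24.9%) |
| 23 | 0% (0 to 14.8%) | 4.3% (0.1 to 21.9%) |

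The counts of 16 and 20 are patients evaluable at Day 56. AE rates use the Safety set (SAP 7.3 and 7.8.1), which may be larger. The row for 23 shows the effect of a larger denominator.

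**The case against.** The strongest reply is that little would be hidden. Table 14.3.2 lists deaths and other SAEs in the Safety set, and its title is not limited to TEAEs. Listings 16.2.7.1 and 16.2.7.2 cover AEs and SAEs. The laboratory, ECG and vital-sign endpoints do not use the TEAE flag. A reader might infer that a worsening event disappears from every primary safety output, and the documents do not support that. What stands is narrower: a listing gives no incidence, and tables 14.3.1.1 to 14.3.1.8 would omit the event.

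The loss is also conditional. Taken literally, SAP 7.8 would count a new report made after dosing. The Protocol sentence on SAE onset belongs to a reporting instruction, and nothing says it sets the TEAE flag. The CRF may open a new record at a change in severity. All of this is fair, but it leaves the outcome to documents that the SAP does not cite for this purpose.

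A reader might also take the condition in SAP 7.8.2 that the start is on or after the first dose as removing missing-month events from the TEAE tables. It does not: it governs only the calculation of onset day. Nor does the missing-day rule lose true post-dose events, since step 3 shows that it over-counts. The negative duration is uncertain too, because 7.8.2 calculates duration only when both dates are complete and does not say whether a substituted date qualifies. Data queries may also resolve some dates.

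Finally, any one patient is worth 5 or 6 points in any table, and no test depends on the count. That is correct, so the size shows sensitivity and is not evidence of bias.

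**Conclusion.** The point holds in this limited form. The two TEAE rules conflict and neither has a clause for worsening or a change to serious. The same-month substitution lacks a stop-date check, missing-month events have no class under SAP 4.9.1, and SAP 7.1.2 and 7.7 contradict 7.8.2. The effect is confined to the TEAE incidence tables. The loss of worsening events rests on three conditions: that 4.9.1 is the rule applied, that the original onset date is kept, and that no new CRF record is opened.

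The documents give no rate for such events, so the number affected is unknown. Each misclassified patient moves an incidence by 6.3 points of 16 or 5.0 of 20, and by less in a larger Safety set. No sample-size figure changes. The change should be made, because the affected tables report the first primary endpoint and the remedy is small.

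**What to change.** - **One definition** in SAP 4.9.1, 7.8 and 7.8.2: an AE with onset on or after the first injection, or an AE with earlier onset that increases in severity or becomes serious on or after it. Identify the change from the CRF or SAE-form data available.
- **Stop-date check** in 7.8.2: substitute the first-dose date only when the stop date is not before the first dose.
- **Default for incomplete dates**: treat an event with a partial or missing start date as treatment emergent unless the known dates show that it was before the first injection.
- **Imputation sentence** in 7.1.2 and 7.7: no imputation other than the AE date rules of 7.8.2.

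The cost is SAP wording and a small change to derivation code. TEAE counts may rise slightly. The date of worsening may have to be taken from existing records. The SAE form in Protocol Appendix 5 asks for a dated chronology with severity, but the CRF items listed in Protocol section 9 do not include a date of severity change, so non-serious worsening may be harder to place. The SAP is dated January 2018, after the planned end of recruitment in September 2017, so new collection should not be assumed.
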